## **5.5 Patient Input on Study Design**

No patient input was obtained for this study design.

## **6. Study Population**

Investigators will be expected to maintain a screening log of all potential study candidates that includes limited information about the potential candidate (eg, date of screening).

Eligibility criteria will be evaluated during screening. Eligibility labs are to be confirmed by central laboratory prior to enrollment.

Before any study-specific activities/procedures, the appropriate written informed consent must be obtained (see Section [12.3](#)).

Prospective approval of protocol deviations to recruitment and enrollment criteria, also known as protocol waivers or exemptions, will not be provided.

## **6.1 Inclusion Criteria**

All screening laboratory assessments must be done in accordance with [Table 12-1](#). Local laboratory assessments may not be used in place of central laboratory assessments where required.

Subjects are eligible to be included in the study only if all the following criteria apply:

- 101 Subject has provided informed consent prior to initiation of any study-specific activities or procedures or subject's legally acceptable representative has provided informed consent prior to any study-specific activities/procedures being initiated when the subject has any kind of condition that, in the opinion of the Investigator, may compromise the ability of the subject to give written informed consent.
- 102 Males or females  $\geq$  18 years of age.
- 103 Subject has multiple myeloma with documented relapse or progression after most recent myeloma treatment. Subjects refractory to the most recent line of therapy are eligible, unless last treatment contained PI or lenalidomide and dexamethasone.
  - Refractory is defined as disease that is nonresponsive or progresses within 60 days of last therapy
- 104 Subjects must have at least PR to at least 1 line of prior therapy.
- 105 Subjects must have received at least 1 but not more than 3 prior lines of therapy for multiple myeloma (induction therapy followed by stem cell transplant and consolidation maintenance therapy will be considered as 1 line of therapy). See Section [12.8](#) for guidelines for documenting prior treatment.
- 106 Prior therapy with a PI is allowed if the patient achieved at least a PR to most recent treatment with a PI, did not relapse within 60 days of discontinuation of the PI and the PI was not removed due to toxicity. A history of prior neuropathy is permitted if this was not grade 3, grade 4 or grade 2 with pain and if not resolved within the 14 days before enrollment, is less than or equal to grade 2 without pain.
- 107 Prior therapy with a lenalidomide and dexamethasone containing regimen is allowed if the patient achieved at least a PR to most recent treatment with lenalidomide and dexamethasone, did not progress within the first 3 months of initiating a lenalidomide and dexamethasone containing treatment or relapse within 60 days of discontinuation of lenalidomide and dexamethasone containing treatment and treatment was not discontinued due to toxicity. A history of prior

neuropathy is permitted if this was not grade 3, grade 4 or grade 2 with pain and if not resolved within the 14 days before enrollment, is less than or equal to grade 2 without pain. Patients are permitted to have received single agent lenalidomide as maintenance therapy within 60 days of enrollment.

108 Measurable disease with at least 1 of the following assessed within 28 days prior to randomization:

- IgG multiple myeloma: serum monoclonal protein (M-protein) level  $\geq 1.0$  g/dL
- IgA, IgD, IgE multiple myeloma: serum M-protein level  $\geq 0.5$  g/dL
- urine M-protein  $\geq 200$  mg per 24 hours
- in subjects without measurable serum or urine M-protein, serum-free light chain (SFLC)  $\geq 100$  mg/L (involved light chain) and an abnormal serum kappa lambda ratio

109 Eastern Cooperative Oncology Group Performance Status (ECOG PS) of  $\leq 2$  (see Section 12.9).

## **6.2 Exclusion Criteria**

Subjects are excluded from the study if any of the following criteria apply:

### **Disease-related**

201 Waldenström macroglobulinemia.

202 Multiple myeloma of IgM subtype.

203 POEMS syndrome (polyneuropathy, organomegaly, endocrinopathy, monoclonal protein, and skin changes).

204 Plasma cell leukemia ( $> 2.0 \times 10^9/L$  circulating plasma cells by standard differential).

205 Primary amyloidosis (patients with multiple myeloma with asymptomatic deposition of amyloid plaques found on biopsy would be eligible if all other criteria are met).

206 Myelodysplastic syndrome.

### **Other Medical Conditions**

207 History of other malignancy within the past 5 years, with the following exceptions:

- Malignancy treated with curative intent and with no known active disease present for  $\geq 3$  years before enrollment and felt to be at low risk for recurrence by the treating physician
- Adequately treated non-melanoma skin cancer or lentigo maligna without evidence of disease
- Adequately treated cervical carcinoma in situ without evidence of disease
- Adequately treated breast ductal carcinoma in situ without evidence of disease
- Prostatic intraepithelial neoplasia without evidence of prostate cancer

- Adequately treated urothelial papillary noninvasive carcinoma or carcinoma in situ
- Treated medullary or papillary thyroid cancer
- Similar neoplastic conditions with an expectation of > 95% 5-year disease-free survival

208 Known HIV infection, hepatitis C infection (subjects with hepatitis C that achieve a sustained virologic response after antiviral therapy are allowed), or hepatitis B infection (subjects with hepatitis B surface antigen or core antibody that achieve sustained virologic response with antiviral therapy are permitted with a requirement for regular monitoring for reactivation for the duration of treatment on the study).

209 Ongoing graft-vs-host disease.

210 Acute active infection requiring systemic antibiotics, antifungal, antiviral (except antiviral therapy directed at hepatitis B) agents within 14 days prior to randomization.

211 Known cirrhosis.

212 Significant neuropathy (grades 3 to 4, or grade 2 with pain) within 14 days prior to randomization.

213 Subjects with pleural effusions requiring thoracentesis or ascites requiring paracentesis within 14 days prior to randomization.

### **Cardiopulmonary Conditions**

214 Uncontrolled hypertension, defined as a subject whose blood pressure **is greater than or equal to** 160 mmHg systolic or **greater than or equal to** 100 mmHg diastolic when taken in accordance with the European Society of Hypertension/European Society of Cardiology 2018 guidelines (Section 12.10; Williams et al, 2018).

215 Active congestive heart failure (New York Heart Association Class III to IV), symptomatic ischemia, uncontrolled arrhythmias, screening ECG with corrected QT interval (QTc) of > 470 msec, pericardial disease, or myocardial infarction within 4 months prior to randomization.

216 Intolerance to hydration due to pre-existing pulmonary or cardiac impairment.

217 History of interstitial lung disease or ongoing interstitial lung disease.

### **Prior/Concomitant Therapy**

218 Immunotherapy within 28 days prior to randomization.

219 Monoclonal antibody therapy within 28 days prior to randomization.

220 Chemotherapy with approved anticancer therapeutic within 28 days prior to randomization.

221 Glucocorticoid therapy within 14 days prior to randomization that exceeds a cumulative dose of 160 mg of dexamethasone or equivalent dose of other corticosteroids.

- 222 Focal radiation therapy within 7 days prior to randomization. Radiation therapy to an extended field involving a significant volume of bone marrow within 28 days prior to randomization (ie, prior radiation must have been to < 30% of the bone marrow).
- 223 Major surgery (except kyphoplasty) within 28 days prior to randomization.
- 224 Autologous or allogeneic stem cell transplant within 90 days prior to randomization.
- 225 Contraindication or intolerance to lenalidomide, dexamethasone, or carfilzomib.
- 226 Known history of allergy to Captisol (a cyclodextrin derivative used to solubilize carfilzomib).
- 227 Subject has known hypersensitivity to any of the products or components to be administered during dosing, including hypersensitivity to antiviral drugs.

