#### **7.1.4.6 Bisphosphonate or Monoclonal Antibody Therapy**

Concomitant therapy should be administered to all subjects with evidence of lytic destruction of bone or with osteopenia (Gralow et al; 2013; Terpos et al, 2013) unless

contraindicated. Commercially available therapies are preferred when available and should be used for subjects with osteolytic or osteopenic myelomatous bone disease according to the manufacturer's recommendations, as described in the prescribing information.

Subjects who are using bisphosphonate or monoclonal antibody therapy when they enter the study should continue the same treatment. Subjects with evidence of lytic destruction of bone or with osteopenia who are not using a bisphosphonate or monoclonal antibody therapy at the time of randomization should start therapy as soon as possible during cycle 1 or 2 of treatment. Investigators should not start bisphosphonate or monoclonal antibody therapy during the study, unless it has been agreed with the sponsor that there is no sign of disease progression.

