#### **7.1.7 Excluded Treatments, Medical Devices, and/or Procedures During Study Period**

##### **7.1.7.1 Anticancer Therapeutic or Radiation**

Concurrent therapy with a marketed or investigational anticancer therapeutic or radiation to large marrow reserves for either a palliative or therapeutic intent is excluded.

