## **9. Study Assessments and Procedures**

Study procedures and their time points are summarized in the Schedule of Activities (see [Table 2-1](#)).

As protocol waivers or exemptions are not allowed if an enrolled subject is subsequently determined to be ineligible for the study, this must be discussed with the sponsor immediately upon occurrence or awareness to determine if the subject is to continue or discontinue study treatment.

Adherence to the study design requirements, including those specified in the Schedule of Activities, is essential and required for study conduct.

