### **9.1 General Study Periods**

#### **9.1.1 Screening, Enrollment and/or Randomization**

Informed consent must be obtained before completing any screening procedure or discontinuation of standard therapy for any disallowed therapy. After the subject has signed the ICF, the site will register the subject in the IxRS and screen the subject to assess eligibility for participation. The screening window is up to 28 days from date of consent until randomization.

All screening evaluations must be completed and reviewed to confirm that potential subjects meet all eligibility criteria. The investigator will maintain a screening log to record details of all subjects screened and to confirm eligibility or record reasons for screening failure (see [Section 6.4](#)), as applicable.

If a subject has not met all eligibility criteria at the end of the screening period, the subject will be registered as a screen fail. Screen fail subjects may be eligible for rescreening 1 time.

Rescreen subjects must first be registered as screen failures in IxRS and subsequently registered as rescreens. Once the subject is registered as rescreened, a new 28-day screening window will begin. Subjects will retain the same subject identification number assigned at the original screening. If the rescreening period begins more than 28 days after the original signing of the ICF, all screening procedures, including informed consent, must be repeated.

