6.3 Per Protocol Set

The per-protocol population will include all randomized subjects who do not have any major protocol deviations that might affect the interpretation of the analyses of the efficacy endpoints. Subjects with the following important protocol deviation (IPD) will be excluded from the per protocol set.

- Major inclusion criteria not met (103 - 109 in protocol):
 - Documented relapse or progression after the most recent myeloma treatment. Subjects refractory to the most recent line of therapy are eligible, unless the last treatment contained PI or lenalidomide and dexamethasone) (103)
 - Subjects must have at least PR to at least 1 line of prior therapy (104)
 - Subjects must have received at least 1 but not more than 3 prior lines of therapy for multiple myeloma (induction therapy followed by stem cell transplant and consolidation maintenance therapy will be considered as 1 line of therapy) (105)

- Inclusion criteria of prior therapy with PI (106)
- Inclusion criteria of prior therapy with a lenalidomide and dexamethasone containing therapy (107)
- Inclusion criteria of measurable disease (108)
- Eastern Cooperative Oncology Group Performance Status (ECOG PS) of $0 \leq 2$ (109)
- Major exclusion criteria not met

Disease related (201 - 206 in protocol):

- Waldenström macroglobulinemia (201)
- Multiple myeloma of IgM subtype (202)
- POEMS syndrome (polyneuropathy, organomegaly, endocrinopathy, monoclonal protein, and skin changes) (203)
- Plasma cell leukemia ($> 2.0 \times 10^9/L$ circulating plasma cells by standard differential) (204)
- Primary amyloidosis (patients with multiple myeloma with asymptomatic deposition of amyloid plaques found on biopsy would be eligible if all other criteria are met) (205)
- Myelodysplastic syndrome (206)

Other medical conditions (207 - 211 in protocol):

- History of other malignancy within the past 5 years (other than protocol specified exceptions) (207)
- Known HIV infection, or uncontrolled hepatitis B or C infection (subjects without sustained virologic response) (208)
- Ongoing Graft versus host disease (209)
- Acute active infection requiring systemic antibiotics, antifungal, antiviral agents (except antiviral therapy directed at hepatitis B) within 14 days prior to randomization (210)
- Known cirrhosis (211)

Cardiopulmonary considerations (214 - 215 in protocol):

- Uncontrolled hypertension (214)
- Active congestive heart failure (New York Heart Association Class III to IV) (215)

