Prior or concomitant therapy (218 - 222, 228 in protocol):

- Immunotherapy, monoclonal antibody therapy or approved anti-cancer chemotherapy within 28 days prior to randomization (218, 219, 220)
- Glucocorticoid therapy exceeding a cumulative dose of 160mg within 14 days prior to randomization (221)
- Focal radiation therapy within 7 days prior to randomization, radiation to large marrow reserves within 28 days (i.e., prior radiation must have been to <30% of the bone marrow) (222)
- Currently receiving treatment in another investigational device or drug study within 28 days of randomization (228)

Organ Function Assessment:

- Calculated or measured creatinine clearance < 30 mL/min (calculation must be based on the Cockcroft and Gault formula) within 28 days prior to randomization (244)
- Major treatment non-compliance
 - Treatment received different from treatment randomized (IPD Criteria 500).
 - Incorrect carfilzomib dose: under-dosing that meets IPD Criteria 502.
 - Failure to obtain extramedullary plasmacytoma assessment and /or bone lesion assessment as part of baseline disease assessment such that the primary endpoint cannot be assessed (IPD Criteria 801).
 - Any C1D1 disease assessment or disease specific lab required at baseline is missed or collected in such a way that patient is not measurable as defined per protocol (IPD Criteria 802).
 - Failure to obtain 2 consecutive disease response assessments that may impact the assessment of the primary endpoint (IPD Criteria 803).

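### Exclusion 219 bars any monoclonal antibody in the 28 days before randomization, with no exception for the bone-directed antibody therapy that Section 7.1.4.6 tells subjects to continue

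*Protocol*

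**What the plan says.** Exclusion 219 (Protocol 6.2, Prior/Concomitant Therapy) reads: "Monoclonal antibody therapy within 28 days prior to randomization". No drug, purpose or exception is stated.

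Section 7.1.4.6 deals with bone disease. It says: "Concomitant therapy should be administered to all subjects with evidence of lytic destruction of bone or with osteopenia", unless contraindicated. For those already treated it says: "Subjects who are using bisphosphonate or monoclonal antibody therapy when they enter the study should continue the same treatment". It names no antibody; the bone purpose comes from the indication it gives.

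These provisions bear on how the two meet:

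- Protocol 6 states that deviations from enrolment criteria will not be approved in advance.
- Protocol 9.1.1: "The screening window is up to 28 days from date of consent until randomization".
- Protocol 9, on an enrolled subject later found ineligible: "this must be discussed with the sponsor immediately upon occurrence or awareness to determine if the subject is to continue or discontinue study treatment".
- SAP 6.3: "Subjects with the following important protocol deviation (IPD) will be excluded from the per protocol set". The list that follows has an item reading "Immunotherapy, monoclonal antibody therapy or approved anti-cancer chemotherapy within 28 days prior to randomization (218, 219, 220".

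Neither document contains a sentence that reconciles 219 with 7.1.4.6.

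**The concern.** The same term appears in an eligibility bar and in a supportive-care instruction, and the two point in opposite directions for a recently dosed subject. A patient with lytic disease who is up to date with a bone-directed antibody is someone 7.1.4.6 expects to enrol and keep on treatment. Exclusion 219, as worded, turns that patient away.

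A site facing such a patient has three choices: record a screen failure, hold back an indicated bone dose until the window has passed, or enrol against the literal criterion. Different sites could choose differently. If a subject is enrolled and later judged ineligible, Section 9 opens a discussion about stopping study treatment, over a drug the protocol itself says to continue. What is at stake is consistent eligibility, appropriate bone care and, at one remove, membership of the per-protocol set. The primary inference is not at stake.

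**Working it through.** The check is a comparison of texts, with one piece of date arithmetic. The plan gives no figure to reproduce.

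1. **Who is caught.** Let *d* be the days from the last bone-antibody dose to randomization. Exclusion 219 is breached when *d* ≤ 28. When *d* > 28, the subject meets 219 and can continue the antibody on study under 7.1.4.6, so both sections are satisfied.

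2. **Doses during screening.** Section 9.1.1 allows at most 28 days from consent to randomization. A dose given *s* ≥ 1 days after consent, in the screening period that ends in randomization, has *d* ≤ 28 − *s* ≤ 27. Every such dose falls inside the 219 window. Continuing the antibody on schedule during screening can therefore make an otherwise eligible subject ineligible.

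3. **Who is not caught.** Bisphosphonates are not antibodies, so 219 does not touch them. Subjects with bone disease who are untreated at randomization and start in cycle 1 or 2, as 7.1.4.6 directs, start after the window.

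4. **Whether nearby text limits 219.** Exclusion 220 is limited to approved anticancer agents. Exclusion 223 exempts kyphoplasty. Exclusion 210 exempts hepatitis B antivirals. The on-study rule in 7.1.7.1 is also limited: "Concurrent therapy with a marketed or investigational anticancer therapeutic or radiation to large marrow reserves for either a palliative or therapeutic intent is excluded". Limits are written where they are meant, and 219 has none.

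5. **Route to the per-protocol set.** SAP 6.3 removes a subject only for an important protocol deviation. SAP 9.3 takes eligibility deviations from the protocol and lets the deviation categories be updated up to database lock. SAP 7.3 then says per-protocol sensitivity analyses might be run only if that set is below 90% of the intent-to-treat population. With 460 randomized, 0.90 × 460 = 414, so the set would have to fall to 413 or fewer: at least 460 − 413 = 47 exclusions for all reasons combined. SAP 8.3 mentions a per-protocol analysis of missing assessments without repeating that condition.

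6. **Route to the main analyses.** None. The intent-to-treat set is all randomized subjects (SAP 6.1), and 219 enters neither the synthesis test nor the sample-size calculation.

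**The case against.** The best reply is that the intent is plain from context. Exclusion 219 sits between immunotherapy and anticancer chemotherapy, in a run that goes on to radiation and transplant. SAP 6.3 puts 218, 219 and 220 in one item. Section 7.1.4.6 is the more specific provision and assumes that subjects already on bone antibodies will enter. On study, 7.8.2 allows any supportive care that 7.1.7 does not list. The two rules also cover different periods, before and after randomization, and continuing a treatment need not mean a dose inside the 28 days.

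Much of this stands. Antimyeloma antibodies are the likely target, and the difference in periods is why the conflict is only partial. But the limit is not in the text, and without waivers a site that reads 219 literally has no route to enrol the subject. No documented case shows sites diverging; that remains a risk, not a finding.

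A reader might infer three stronger things:

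- **That 219 makes 7.1.4.6 void.** It does not, given steps 1 and 3 of the working.
- **That the share of bone-antibody users caught can be stated.** That share depends on the dosing interval, which the documents do not give, and any percentage would apply to a group of unknown size.
- **That every breach removes a subject from the per-protocol set and weakens the non-inferiority conclusion.** Removal is conditional, and the per-protocol set serves only sensitivity analyses.

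**Conclusion.** The point holds as a minor inconsistency. It is more than a missing detail: for a subject given a bone-directed antibody within 28 days before randomization, the stated rule produces either exclusion or a withheld dose, against the protocol's own supportive-care instruction. This rests on reading 219 literally and on taking the antibody therapy in 7.1.4.6 to be bone-directed, as its indication implies.

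The number of subjects affected cannot be derived from the documents. There is no effect on the intent-to-treat tests, the sample size, the significance level or the power. Any effect on per-protocol sensitivity analyses is conditional and unquantified.

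A reader might also infer that 219 should be restricted to antimyeloma or anticancer antibodies. The documents do not support going that far. That wording would also admit unrelated non-anticancer antibodies, such as immunosuppressive ones, and nothing shows that the sponsor wants them allowed in the washout period. Section 7.1.7.1 is an on-study rule and does not settle eligibility.

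**What to change.** Add to exclusion 219: *except bone-directed antibody therapy given under Section 7.1.4.6*. Add the same exception to the 219 part of the prior-therapy item in SAP 6.3, so that a subject who follows 7.1.4.6 is not counted as a deviation.

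The cost is a few words in one criterion and one SAP item. It needs no new data or procedures and leaves the sample size, alpha and intent-to-treat analyses as they are. If enrolment has already closed, the protocol change no longer affects who enters, but the SAP exception still matters for classifying deviations and should be settled before database lock.

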#### **Prior/Concurrent Clinical Study Experience**

- 228 Currently receiving treatment in another investigational device or drug study, or < 28 days since ending treatment on another investigational device or drug study(ies).

